# **Protocol Amendment Summary of Changes Table**

DOCUMENT HISTORY	
Document	Date
Original Protocol	22 Jan 2020

#### 1. PROTOCOL SUMMARY

#### 1.1. Synopsis

**Protocol Title:** Single-Arm Study of Lorlatinib in Participants with Anaplastic Lymphoma Kinase (ALK)-Positive Non-Small Cell Lung Cancer (NSCLC) Whose Disease Progressed After One Prior Second-Generation ALK Tyrosine Kinase Inhibitor (TKI)

**Short Title:** Study of Lorlatinib In Participants with Anaplastic Lymphoma Kinase (ALK) -Positive NSCLC

#### **Rationale:**

On the basis of pivotal Phase 1/2 study B7461001, lorlatinib received Conditional Marketing Authorization (CMA) by the European Medicine Agency (EMA) on 7 May 2019 for the treatment of patients with ALK-positive metastatic non-small-cell lung cancer whose disease has progressed after:

- alectinib or ceritinib as the first ALK tyrosine kinase inhibitor (TKI) therapy; or
- crizotinib and at least one other ALK inhibitor.

However, in view of the limited sample size of 28 patients post second generation ALK TKI from the pivotal phase 1/2 study B7461001, in addition to the ongoing Phase 3 study B7461006 (CROWN), the EMA requested a post-authorization efficacy study (PAES) to obtain additional data on the activity of lorlatinib in the second-line setting.

### **Objectives, Estimands and Endpoints**

Objectives	Estimands	Endpoints
Primary		
To assess Overall and Intracranial Response Rate of single-agent lorlatinib in participants with advanced ALK-positive NSCLC whose disease has progressed on alectinib or ceritinib as the first ALK tyrosine kinase inhibitor (TKI) therapy	The primary estimand is the treatment effect of lorlatinib by independent central review (ICR) from time of first dose until progression is met or subsequent anticancer therapy is administered for all participants who receive at least one dose of lorlatinib without regard to discontinuation from treatment	Confirmed Objective     Tumor Response     assessed by Response     Evaluation Criteria in     Solid Tumor (RECIST)     version 1.1 per ICR
Secondary		

- To assess secondary measures of clinical efficacy
- The estimand for
   Objective Response
   (OR) by investigator
   (INV) follows the
   estimand specified for
   the primary endpoint
   except that the treatment
   effect is based on INV
- The estimand for Intracranial (IC) response is the Intracranial treatment effect (ie in brain lesions) of lorlatinib from time of first dose until Intracranial progression is met or subsequent anti-cancer therapy is administered for all participants who receive at least one dose of lorlatinib without regard to discontinuation from treatment
- The estimand for Time to Tumor Response (TTR) is the treatment effect from the time of first dose to the first date of response that is subsequently confirmed for responders to lorlatinib
- The estimand for Duration of Response (DOR) is the treatment effect from the first date of OR that is subsequently confirmed for responders to lorlatinib until progression or death, without regard to discontinuation from

- Every endpoint assessed by RECIST version 1.1
- Confirmed Objective Tumor Response assessed by INV
- Confirmed Intracranial tumor response assessed per ICR and INV
- TTR per ICR and INV
- DOR per ICR and INV
- Duration of Intracranial response (IC-DOR) per ICR and INV
- TTP per ICR and INV
  - PFS per ICR and INV

- treatment unless new anti-cancer therapy is initiated or extended gap in tumor assessment is present prior to progression or death
- The estimand for IC-DOR follows the estimand specified for the DOR, but limited to intracranial lesions
- The estimand for Time to Tumor Progression (TTP) is the treatment effect from the time of first dose for all participants who receive at least one dose of lorlatinib until progression, without regard to discontinuation from treatment unless participant dies, new anti-cancer therapy is initiated or extended gap in tumor assessment is present prior to progression
- Progression Free
  Survival (PFS) is the
  treatment effect from the
  time of first dose for all
  participants who receive
  at least one dose of
  lorlatinib until
  progression or death,
  without regard to
  discontinuation from
  treatment unless new
  anti-cancer therapy is
  initiated or an extended
  gap in tumor assessment

	is present prior to progression or death	
To confirm the safety and tolerability of lorlatinib	• The estimand for safety is the incidence of Adverse Events from the time of first dose to 28 days post last dosing date or the date of initiation of a new anticancer therapy for all participants who receive at least one dose of lorlatinib	• Adverse Events as characterized by type, frequency, severity (as graded by National Cancer Institute Common Terminology Criteria for Adverse Events [NCI CTCAE] v.4.03), seriousness, and relationship to study therapy

## **Overall Design:**

This is a Phase 4 open-label, multi center, multi-national, non-randomized, prospective, single-arm study of lorlatinib in adult participants with ALK-positive NSCLC who progressed on alectinib or ceritinib as first line of treatment for metastatic disease.

## **Disclosure Statement:**

This is a Single Group Treatment study with 1 Arm that has No masking.

### **Number of Participants:**

Approximately 85 participants will be screened to achieve 70 participants assigned to study intervention.

### **Intervention Groups and Duration:**

Participants will take lorlatinib at the approved dose of 100 mg QD (once daily). Participants will be treated until disease progression, participant refusal/lost to follow-up, or unacceptable toxicity.

**Data Monitoring Committee:** No

## 1.2. Schema

Adult participants with ALK+ NSCLC whose disease progressed after one prior second-generation ALK TKI

Lorlatinib 100 mg once dailyb

- a alectinib or certinib
- b Treatment until disease progression, patient refusal/lost to follow-up, or unacceptable toxicity.

## 1.3. Schedule of Activities (SoA)

The schedule of activities table provides an overview of the protocol visits and procedures. Refer to Section 8 of the protocol for detailed information on each assessment required for compliance with the protocol.

The Investigator may schedule visits (unplanned visits) in addition to those listed in the schedule of activities table in order to conduct evaluations or assessments required to protect the well-being of the participant.

## 1.3.1. Screening and Cycle 1

Visit Identifier	Screening*	Cycle 1 (21 days)	Notes  *to be obtained within 28 days prior to registration
Visit Window	≤28 days	Day 1 (±1 day)	(X) refer to specific footnote when the measurement may be optional /repeat measurement might not be required.
Informed consent	X		Must be obtained prior to undergoing any study specific procedures that are not considered standard of care.
Tumor history	X		
Medical history	X		Data on prior anti-cancer therapy will be collected along with the best-known response from the previous ALK inhibitor.
Physical examination	X	X	
Weight	X	X	
Performance Status	X	X	
Contraception check (as appropriate)		X	
Laboratory	·		
Hematology	X	(X)	No need to repeat on C1D1 if baseline assessment performed within 7 days prior to that date. For those visits after C1D1, hematology labs should be performed according to lorlatinib product information.

Visit Identifier	Screening*	Cycle 1 (21 days)	Notes  *to be obtained within 28 days prior to registration
Visit Window	≤28 days	Day 1 (±1 day)	(X) refer to specific footnote when the measurement may be optional /repeat measurement might not be required.
Blood Chemistry	X	(X)	No need to repeat on C1D1 if baseline assessment performed within 7 days prior to that date. For those visits after C1D1, blood chemistry should be performed according to lorlatinib product information.
Pregnancy test	X	(X)	For female participants of childbearing potential, a serum or urine pregnancy test will be performed once at the start of screening and once at the baseline visit, immediately before study intervention administration. The pregnancy test should be performed at the clinical site's local laboratory.
Cardiac Monitoring	 		
12-lead ECG	X	(X)	No need to repeat on C1D1 if baseline assessment performed within 7 days prior to that date. During study treatment additional triplicate ECGs may be performed as clinically indicated and according to lorlatinib product information.
LVEF Assessment	X		Echocardiogram or MUGA will be performed. During study treatment additional assessments may be performed as clinically indicated and according to lorlatinib product information.
			For France and Germany, a transthoracic echocardiogram (TTE) will be performed every 6 months (± 2 weeks) during treatment, and only at the end of treatment visit if the previous assessment was > 1 month. Pulmonary arterial pressure (PAP) will be assessed.
Registration	·		
Registration		(X)	Registration will be within 2 days prior to study treatment start.
Tumor Assessments			
CT and MRI Scan or Equivalent	X		Tumor assessments will include all known or suspected disease sites. CT or MRI scans of Chest Abdomen Pelvis [CAP] and MRI of the brain will be performed at screening. Bone scans (or bone MRI if preferred by investigator) will be performed at baseline for all participants and repeated every 12 weeks on study only if evidence of bone metastases is observed at baseline.

Visit Identifier	Screening*	Cycle 1 (21 days)	Notes  *to be obtained within 28 days prior to registration	
Visit Window	≤28 days	Day 1 (±1 day)	(X) refer to specific footnote when the measurement may be optional /repeat measurement might not be required.	
Cerebrospinal fluid if leptomeningeal/carcinomatous meningitis [LM/CM] disease is present	X		CSF is mandatory for participants who have asymptomatic radiologically suspected leptomeningeal disease (LM) or carcinomatous meningitis (CM) but negative spinal fluid.	
Other Clinical Assessments	Other Clinical Assessments			
Adverse Events	X	X	For AEs and SAEs, the active reporting period to Pfizer or its designated representative begins from the time that the participant provides informed consent, which is obtained prior to the participant's participation in the study through and including a minimum of 28 calendar days after the last administration of the study intervention. Refer to Section 8.3.1 for all specifications.	
Concomitant medications and non- drug supportive interventions	X	X		

## 1.3.2. Visits on Day 1 of Every Other Cycle (up to 35 cycles and >35 cycles)

Visit Identifier	Visits on Day 1 of Every Other Cycle up to 35 cycles (up to 24 months)	Visits on Day 1 of Every Other Cycle (> 35 cycles or 24 months)	Notes  (X) refer to specific footnote when the measurement may be optional /repeat measurement might not be required.
Visit Window	±4 days	±4 days	
Physical examination	X		
Weight	X		
Contraception check (as	X	X	At cycle not requiring site visit the participant may be contacted by phone to
appropriate)	(every cycle ±2 days)	(every cycle ±2 days)	confirm contraception is still appropriate per the protocol.
Laboratory			

Visit Identifier	Visits on Day 1 of Every Other Cycle up to 35 cycles (up to 24 months)	Visits on Day 1 of Every Other Cycle (> 35 cycles or 24 months)	Notes  (X) refer to specific footnote when the measurement may be optional /repeat measurement might not be required.
Visit Window	±4 days	±4 days	
Pregnancy test	X (every cycle ±2 days)	X (every cycle ±2 days)	Pregnancy tests will be routinely repeated at every cycle (±2 days) during the active treatment period and additionally whenever one menstrual cycle is missed or when potential pregnancy is otherwise suspected. The pregnancy test should be performed at the clinical site's local laboratory. Where that is not possible, participants will provide the laboratory test results carried out at a non-clinical site laboratory, eg, by telephone, and bring a copy of the laboratory test results at the next cycle visit. The copy of the laboratory test results must be retained in the participants' file at the clinical site for documentation purposes.
Study Intervention			
Study Intervention	Once a day continuously		
Tumor Assessments			
CT and MRI Scan or Equivalent	(every 6 weeks ± 1 week)	(As per local clinical practice)	CT and MRI scans to be done at every 6 weeks ±1 week up to approximately 24 months (cycle 35) and then as per local clinical practice.
Other Clinical Assessments			
Adverse Events	X	X	
Concomitant medications and non-drug supportive interventions	X		All concomitant medications and non-drug supportive interventions should be recorded in the CRF until the participant has completed 35 cycles of treatment (approximately 24 months). After cycle 35 the data will be reported in the medical chart, but not collected in the CRF.

## 1.3.3. End of Treatment and Follow-Up

**End of Treatment Visit:** Obtain these assessments if not completed in the last week (last 6 weeks for tumor assessments up to 24 months).

**Follow up:** At least 28 days, and no more than 35 days after discontinuation of treatment participants will return to undergo review for resolution of any treatment related toxicity. Participants continuing to experience toxicity at this point following discontinuation of treatment will continue to be followed at least every 4 weeks until resolution or determination, in the clinical judgment of the Investigator, that no further improvement is expected. Participants discontinuing treatment for reasons other than progression of disease will continue to perform tumor assessments until PD up to approximately 24 months (cycle 35).

Visit Identifier	End of Treatment	Follow-up	Notes  (X) refer to specific footnote when the measurement may be optional /repeat measurement might not be required.	
Visit Window	±2 days	±7 days		
Physical examination	X			
Weight	X			
Contraception check (as appropriate)	X	X	The participant may be contacted by phone to confirm contraception is still appropriate per the protocol. Males and females of childbearing potential must be contacted after study intervention discontinuation to ensure that they continue to use appropriate contraception for at least 98 and 35 days, respectively, after the last dose of study intervention.	
Laboratory				
Pregnancy test	X	X	The pregnancy test should be performed at the clinical site's local laboratory. Where that is not possible, participants will provide the laboratory test results carried out at a non-clinical site laboratory, eg, by telephone, and bring a copy of the laboratory test results at the next cycle visit. The copy of the laboratory test results must be retained in the participant's file at the clinical site for documentation purposes.	
Tumor Assessments				

Visit Identifier	End of Treatment	Follow-up	Notes  (X) refer to specific footnote when the measurement may be optional /repeat measurement might not be required.
Visit Window	±2 days	±7 days	
CT and MRI Scan or Equivalent	(X)		Tumor assessment should be repeated at the end of treatment if more than 6 weeks have passed since the last evaluation. Tumor assessment should not be repeated at the end of treatment if progression occurs when the participant has shifted to the local clinical practice.
Other Clinical Assessments			
Adverse Events	X	X	
Concomitant medications and non-drug supportive interventions	(X)		

Abbreviations: AE = adverse events; CAP = Chest abdomen pelvis; c; CNS = central nervous system; CT = computed tomography; CRF = case report form; CSF = cerebrospinal fluid; C1D1 = cycle 1 day 1; ECG = electrocardiogram; ECOG = Eastern Cooperative Oncology Group; LM = leptomeningeal meningitis; LVEF = left ventricular ejection fraction; MRI = magnetic resonance imaging; MUGA = multigated acquisition; NCI CTCAE = National Cancer Institute common terminology criteria for adverse events; PD = progression of disease; RECIST = Response Evaluation Criteria in Solid Tumors; TTE = transthoracic echocardiogram

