#### 4. STUDY DESIGN

### 4.1. Overall Design

This is a Phase 4 open-label, multi-center, multi-national, non-randomized, prospective, single arm study of lorlatinib in adult participants with ALK-positive NSCLC who progressed on alectinib or ceritinib as first line of treatment for metastatic disease. Approximately 85 participants will be screened to achieve 70 participants assigned to study intervention.

Participants will take lorlatinib at the approved dose of 100 mg QD. Participants will be treated until disease progression per RECIST 1.1, participant refusal/lost to follow-up, or unacceptable toxicity.

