The estimand for IC-DOR by ICR/INV is the treatment effect from the first date of OR that is subsequently confirmed in brain for responders to lorlatinib, until intra cranial progression or death, without regard to discontinuation from treatment unless new anti-cancer therapy is initiated or extended gap in tumor assessment is present prior to intra cranial progression or death. IC-DOR is defined as the time from first documentation of confirmed OR in brain (CR or PR) to the date of first documentation of PD in brain or death due to any cause, whichever occurs first.

The estimand for TTP by ICR/INV is the treatment effect from the time of first dose for all participants who receive at least one dose of lorlatinib until progression, without regard to

discontinuation from treatment unless death occurs, new anticancer therapy is initiated or an extended gap in tumor assessment is present prior to progression. TTP is defined as the time from date of first dose to the date of the first documented PD due to any cause.

The estimand for PFS by ICR/INV is the treatment effect from the time of first dose for all participants who receive at least one dose of lorlatinib until progression or death due to any cause, without regard to discontinuation from treatment unless new anticancer therapy is initiated or an extended gap in tumor assessment is present prior to progression or death. PFS is defined as the time from date of first dose to the date of the first documented disease progression or death due to any cause, whichever occurs first.

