## 9.2. Sample Size Determination

The primary endpoint is Objective tumor response assessed by RECIST version 1.1 per ICR. Analysis of tumor response will be based on both Overall tumor response and on Intra-Cranial tumor response.

OR is defined as a confirmed CR or confirmed PR from the first dose of study treatment until disease progression, start of anticancer therapy or death due to any cause. Both CR and PR must be confirmed by repeat assessments performed no less than 4 weeks after the criteria for response are first met.

ORR is defined as the proportion of treated participants with confirmed CR or confirmed PR per ICR assessment and will be estimated together with its 2-sided exact 95% CI (using an exact Clopper-Pearson CI).

According to literature, platinum-based doublet chemotherapy in patients with ALK + NSCLC refractory to second generation TKIs has an objective response rate of approximately 30%. Setting as target for lorlatinib a response rate of about 43% (as observed in cohort EXP-3B of phase 2 portion of study B7461001), a sample size of 60 participants would result in an exact two-sided 95% CI of the ORR with lower limit of the CI greater than 30%. In order to compensate for a potential 15% drop out rate (participants with death prior to first post-baseline assessment, inadequate baseline assessment, new anticancer therapy started prior to first post-baseline assessment, post-baseline disease assessments missing), the overall sample size for the study is set to 70 participants.

The study will be considered to have met its primary endpoint if the lower limit of the 95% confidence interval around the estimated ORR excludes 30%.

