## 9.5.2. Independent Central Radiological Review

An independent core imaging laboratory will be used in this study. All sites will be required to submit images to the core imaging laboratory for ICR as soon as they are performed at the site so that imaging scans may be read in real time. The requirements of submitting images will be provided to sites by the core imaging laboratory.

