DMB02-GSOP-RF02 4.0 Statistical Analysis Plan Template 01-Nov-2018 PFIZER CONFIDENTIAL Page 29 TMF Doc ID: 98.03

4	No event and withdrawal of consent date ≥ start date OR End of study (EOS) = Subject refused further follow-up	Withdrawal of consent
5	No event and lost to follow-up in any disposition page	Lost to follow-up
6	No event and EOS page present and no adequate post-baseline tumor assessment	No adequate post-baseline tumor assessment
7	No event and none of the conditions in the prior hierarchy are met	Ongoing without an event

^a more than 98 days after last adequate tumor assessment.

The PFS time or censoring time and the reasons for censoring will also be presented in a participant listing.

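### The plan does not say whose progression ends scanning, so PFS, TTP and DoR per ICR, and intracranial DoR, can be censored at a progression they do not count, under a misleading label

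*Protocol*

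**What the plan says.** **Stopping treatment and scans**
- Protocol 4.1: "Participants will be treated until disease progression per RECIST 1.1". No reader is named.
- Protocol 1.3.3: "Participants discontinuing treatment for reasons other than progression of disease will continue to perform tumor assessments until PD", up to about 24 months. The follow-up column of the schedule holds no CT or MRI. An end-of-treatment scan is due only if the last one is more than 6 weeks old.
- Protocol 7.1: a participant who permanently stops study drug stays in the study for the assessments still scheduled.
- SAP 2.2: follow-up after treatment lasts up to 35 days, and nothing longer is collected.
- SAP 6.2.7 and 6.2.8: six-weekly scans run to progression whether or not another anti-cancer therapy has begun. Again no reader is named.
- Protocol 9.5.2: images are sent promptly to the core laboratory "so that imaging scans may be read in real time". No text makes that read a condition for ending treatment or scanning.

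**Endpoints and censoring**
- PFS, TTP and DoR are analysed per ICR and per investigator.
- Protocol 9.1.1 runs intracranial DoR (IC-DoR) "until intra cranial progression or death, without regard to discontinuation from treatment", with exceptions for new anti-cancer therapy and an extended assessment gap.
- SAP 6.2.6 applies the PFS censoring rules to IC-DoR. SAP 2.1.2 does not list extracranial progression among its intercurrent events.
- SAP 6.2.7 censors a living participant without progression at the last adequate assessment. Row 7 of Table 3, the last row, takes "No event and none of the conditions in the prior hierarchy are met" and reports it as ongoing without an event. Row 8 of Table 5 does the same for TTP.

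**The concern.** Two groups can lose the event for which they are being followed.

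- **Investigator progression that ICR does not call.** If the investigator's call stops lorlatinib, no further scan is scheduled, so ICR has nothing more to read. Reader disagreement is foreseen: Protocol section 3 provides for independent adjudication of investigator-reported events, and SAP 5.2.6 dates the two readings differently.
- **Intracranial responders who progress only outside the brain.** Whole-body progression ends lorlatinib and the planned brain imaging with it, although the IC-DoR estimand continues to brain progression or death.

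Kaplan-Meier estimation assumes that censored participants have the same later risk as those still followed. Here censoring may occur because the disease is worsening. With no control arm, such a bias has nothing to cancel against. The SAP plans 12-month PFS and TTP rates, and the study was requested because earlier evidence in this setting rested on 28 participants. The label is a separate problem. It places people taken off drug for progression in the same row as people still doing well, so the tables would not show how often this happened.

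**Working it through.** **1. The plan's own figures.** No sample size, power or event count is given for PFS, TTP, DoR or IC-DoR. The figures that bear on this point reproduce:
- Extended gap: 2 × 42 + 14 = 98 days, as in SAP 6.2.7.
- Scan limit: 35 × 21 / 30.4375 = 24.1 months, as stated.
- ORR: 26/60 = 43.3%, exact 95% CI 30.6% to 56.8%, in line with Protocol 9.2. ORR has no censoring, because participants without a confirmed response count as non-responders.

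**2. Tracing the text.**

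| | Investigator PD, not ICR PD | Extracranial PD only, intracranial responder |
|---|---|---|
| Scans still scheduled | None beyond a conditional end-of-treatment scan | Same; no brain MRI |
| Effect | PFS, TTP, DoR per ICR censored at about that scan | IC-DoR censored at about that scan, both readers |
| Reason if nothing else is recorded | Table 3 row 7; Table 5 row 8 | Not separately identified |

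The first column reaches row 7 only with adequate baseline and post-baseline scans and no recorded new therapy, withdrawal or loss to follow-up. Row 8 of Table 5 also requires no recorded death. New therapy is collected only up to 35 days after stopping (SAP 5.3.1), so later therapy does not move a participant out of these rows.

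**3. Illustration for the ICR endpoints (assumed inputs).** Take exponential times with median 5.6 months (the DoR in Protocol 2.2), and let a share d of investigator progressions lack an ICR call. If ICR progression would have followed at once, the observed hazard is (1 − d) times the true one, and the median becomes 5.6/(1 − d): 6.2 months at d = 10% and 7.0 at d = 20%. This is an upper-end approximation.

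A simulation is less stark. It used 200,000 participants per scenario, 42-day scans, administrative censoring uniform over 12 to 24 months, ICR calling progression 1, 2 or 4 scans later, and no deaths or new therapy:

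| Share not called by ICR | 12-month rate, scans continued | 12-month rate, as planned |
|---|---|---|
| 0% | 25.5% | 25.5% |
| 10% | 26.1–27.9% | 29.5–29.7% |
| 20% | 26.6–30.4% | 34.1–34.3% |
| 30% | 26.9–32.8% | 39.2–39.5% |

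Matched by lag, the excess is about 2 to 12 points. The median moves from 6.9 to 8.3 months (one scan interval) at 20–30% with a lag of one or two scans. It does not move at 10%, or with a four-scan lag.

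**4. Illustration for IC-DoR (assumed inputs).** Extracranial progression median 5.6 months; brain progression median 8 or 14.5 months; correlation ρ between the two on a normal-copula scale:

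| Brain median | ρ | 12-month rate, scans continued | As planned | Median, continued vs planned (months) |
|---|---|---|---|---|
| 8 | 0 | 38.4% | 38.5% | 8.3 vs 8.3 |
| 8 | 0.3 | 38.5% | 44.5% | 8.3 vs 9.7 |
| 8 | 0.6 | 38.5% | 50.7% | 8.3 vs 12.4 |
| 14.5 | 0 | 59.0% | 58.9% | 15.2 vs 15.2 |
| 14.5 | 0.3 | 59.1% | 65.5% | 15.2 vs 19.3 |
| 14.5 | 0.6 | 59.2% | 73.2% | 15.2 vs not reached |

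With ρ = 0 there is no bias beyond simulation noise. With ρ > 0 the excess is about 6 to 14 points.

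**The case against.** **Protocol 7.1 and SAP 6.2.7 point to continued assessment.** This stands only in part. Protocol 7.1 refers to scheduled assessments, and the schedule holds no scan after progression beyond the conditional end-of-treatment one. SAP 6.2.7 also ends scans at progression without naming a reader. These lines show that the texts need reconciling; they do not close the gap. It also stands that the investigator's role in calling the treatment-stopping progression is inferred.

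**The investigator analyses already count these progressions.** True, and for that reason PFS, TTP and DoR per investigator are largely unaffected. But that analysis replaces every ICR date. It does not isolate the participants on whom the readers differ, and it does not help IC-DoR, which is affected for both readers.

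**Deaths and new therapy limit the effect.** Deaths within 98 days of the last adequate scan, before any new therapy, remain events for PFS, DoR and IC-DoR and offset part of the bias. TTP censors deaths (SAP Table 4). Censoring at new therapy would remain even with longer scanning.

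**The size is assumed.** This stands in full. The earlier DoR median itself has a 95% CI from 4.2 months to not reached.

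**A stronger reading of IC-DoR.** Suppose the total hazard ln2/5.6 is split equally between brain and extracranial progression. The Kaplan-Meier median for brain progression is then 11.2 months, while only 0.5 × (1 − 0.25) = 37.5% have brain progression first by then. A reader might infer that 11.2 months is too long. It is not: with independent constant hazards it is the correct median time to brain progression. The 37.5% is a cumulative incidence that levels off at 50%, which is a different quantity. Shorter medians of 9.3 or 8.3 months arise only if the brain hazard is assumed to double or triple after extracranial progression.

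**Conclusion.** The point holds as a gap in the plan with a known direction and an unknown size. The documents do not say whose progression ends scanning, and Protocol 1.3.3 and 7.1 and SAP 2.2 and 6.2.7 are not reconciled. As written, PFS, TTP and DoR per ICR are censored at an investigator progression that ICR does not call, and IC-DoR is censored at extracranial progression. Under the conditions above, Tables 3 and 5 give the first group a wrong label.

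The estimates are biased upward if the readers disagree and ICR progression would have followed, or if extracranial and brain progression are positively linked. At zero disagreement or zero correlation there is no bias. The excesses of 2 to 12 and 6 to 14 points at 12 months are illustrations on assumed inputs, without deaths or new therapy, and are not predictions.

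A reader might infer that every durability endpoint is inflated by a fixed factor, or that the primary result is at risk. The documents support neither. The affected endpoints are secondary and carry no stated hypothesis, and the ORR decision does not run through this censoring.

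**What to change.** 1. **SAP Tables 3 and 5:** above the ongoing row, add the reason *treatment stopped for investigator PD without ICR PD*. Recorded new therapy ranks higher, so also report the total with investigator but no ICR progression, whatever their censoring reason.
2. **SAP 6.2.5, 6.2.7 and 6.2.8:** add a sensitivity analysis of the ICR endpoints that keeps ICR dates and counts investigator progression as an event where ICR has none.
3. **SAP 6.2.6:** report how many intracranial responders are censored at extracranial progression. Add a sensitivity analysis counting that progression as the end of IC-DoR, labelled a lower bound. The bound can be wide: with independent medians of 8 and 5.6 months it gives 1/(1/8 + 1/5.6) = 3.3 months against a true 8. Cumulative incidence of brain progression may be shown as description. It answers another question and does not correct the bias.
4. **Protocol 1.3.3 and 7.1, SAP 2.2 and 6.2.7–6.2.8:** reconcile these passages and state whose progression ends tumor assessments.

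Items 1 to 3 use data already collected. They cost a few outputs and will give somewhat shorter sensitivity estimates. Item 4 is wording. Longer scanning is not needed for items 1 to 3. It would add procedures, would need therapy dates beyond 35 days, and would leave new-therapy censoring in place.
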